2.3 Sample Size and Power

Formal sample size calculations are not applicable for this proof-of-concept study. The sample size of approximately 100 subjects planned to be entered in this trial is expected to be adequate to provide safety and efficacy information to advise future study design. Subjects who meet all of the inclusion and none of the exclusion criteria will be enrolled in the study until approximately 100 subjects have completed the study.

2.4 Randomization

The trial will be conducted in double blinded, randomized manner with random assignment to standard of care plus brequinar or standard of care plus placebo in a 1:1 ratio at each site. The brequinar and placebo capsules will be provided to each participating institution in pre-numbered bottles intended for individual subjects to be dispensed by the institution's pharmacist or designated person. Randomization assignments will be provided by an independent statistician at Prosoft Clinical to the drug packaging company. The pharmacist/designated person will dispense the next number in sequence to the next patient who qualifies for the study at an individual site.

3. Efficacy and Safety Variables

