Design	
This will be a phase 2 randomized, double blind, multi-center study with approximately 100 subjects. All subjects will receive SOC per relevant guidelines for treatment of out-patients with COVID-19 infection. In addition to SOC, subjects will self-administer one capsule once daily for 5 days.
 
To be eligible for screening, subjects must have a documented positive SARS-CoV-2 test result and have at least one symptom consistent with SARS-CoV-2 infection in the opinion of the investigator. Subjects will have a Screening Visit followed as soon as possible with randomization on Study Day 1. First dose of study drug must take place \leq 7 days from onset of first symptom. Study procedures are presented in detail in the Schedule of Events. Study visits (virtual or in person) will take place at Screening and on Study Days 1 - 8, 12, 15, 22, and 29. The visits that include bloodwork must be conducted at the study site or arrangements made for sample collection at the subject's home or other appropriate location. Other visits/visit activities for that visit may be conducted remotely using telephone, telemedicine or other remote technique. Subjects are to self-collect a viral load sample, obtain their respiratory rate, heart rate, body temperature and SpO₂, and complete a symptom assessment with the site via telemedicine on Days 1, 4, 8, 12, 15, 22, and 29. The site will also have a telephone call with the subject on Study Days 2, 3, 5, 6, and 7 for changes in concomitant medications and assessment of adverse events, especially those that may indicate thrombocytopenia and mucositis. Screening and study Day 1 are to be conducted at the site unless the site is unable to accommodate in-person visits. If the site is unable to accommodate in-person visits, a home visit may be arranged as long as first dose can be achieved within 7 days of symptom onset. Days 8, 15, and 29 require in-person visits and will be conducted via home visit. Any in-person visit may also have telemedicine or telephone components if all study activities cannot be completed in person. Telemedicine only visits will be conducted by site staff on study Days 4, 12, and 22.

Sample Size:	Approximately 100 subjects will be randomized to 5 days of either SOC + brequinar 100 mg or SOC + placebo in a 1:1 ratio (approximately 50 subjects assigned to brequinar 100 mg and 50 subjects to placebo).
Number of Sites:	Approximately 15
Study Period:	An enrollment period of 3 months is expected.

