11.5 Randomization

A randomization scheme will be provided by an independent statistician to the drug packaging company to ensure subjects are randomly assigned to SOC + brequinar or SOC + placebo in a 1:1 ratio.

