11.6 Pooling of Study Centers

Not applicable to this small, early phase study.

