7.2 Subject Disposition and Data Sets Analyzed

Subject disposition will be listed and summarized by treatment group and overall and will include the number and percentage of subjects:

- screened;
- randomized;
- randomized and not treated;
- treated;
- included in each analysis population (ITT, MES, Safety).

In addition, the number and percentage of subjects who complete the study and who discontinue early, including a breakdown of the primary reasons for discontinuation, will be presented for ITT population.

A summary of subject enrollment by site will also be provided.

A summary of the reasons for screen failure as well as the number of subjects screened but not randomized will be produced. No other information for screen failures will be presented.

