7.6 Efficacy

7.6.1 Primary Efficacy Analysis

SARS-CoV-2 Viral load will be reported as below.

- # of copies/mL;
- <# of copies/mL, if detected but under the lower limit of quantification (LLOQ);
- no SARS CoV-2 detected, if not detected.

SARS-CoV-2 Viral load (\log_{10} copies/mL) and change from baseline will be summarized by visit using standard descriptive statistics for the MES population. The baseline value is defined as last scheduled or unscheduled viral load collected prior to the first dose of study drug. For post-baseline, only data from scheduled visits will be included in the summary tables. For the analysis purpose, viral load below the

Statistical Analysis Plan

Sponsor Name: Clear Creek Bio, Inc.
Sponsor Protocol ID: CCB-CRISIS-02

Covance Study ID: 000000207395

LLOQ will be considered equal to the LLOQ. Number of subjects with undetectable SARS-CoV-2 viral load at each visit will be presented as well.

Changes from baseline in SARS-CoV-2 viral load data (\log_{10} copies/mL) will be statistically analyzed using a mixed model for repeated measures (MMRM) in the MES population. The model will contain baseline as a covariate, treatment, day and treatment-by-day interaction as fixed effects. The unstructured covariance matrix will be selected initially; if this analysis fails to converge another covariance structure will be selected based on AIC and BIC values. The least square (LS) means and treatment difference at Days 4, 8, 12, 15, 22 and 29 will be calculated and presented with their corresponding 95% confidence intervals (CIs). All available data will be used in the analysis.

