7.6.2 Secondary Efficacy Analysis

The duration of viral shedding is defined as the time (in days) from Day 1 to the first time where no SARS-CoV-2 is detected. When deriving viral shedding, any missing viral load data will be considered detectable. Subjects will be censored at the last SARS-CoV-2 viral load test if SARS-CoV-2 is detected at all tests.

Kaplan-Meier curves will be used to estimate the distribution of duration of viral shedding in the MES population. The 50th percentile of Kaplan-Meier estimates will be used to estimate the median duration of viral shedding. A two-sided 95% CI will be provided for this estimate. The 25th and 75th percentiles, and the range (minimum, maximum) will be presented as well. The range will be determined including censored observations. Duration of viral shedding will be compared between treatment groups using a unstratified log rank test. The two-sided p-value for the log rank test will be presented.

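### Treatment is assigned 1:1 at each site but the primary model has no site term, so its standard errors are modestly too wide if the list is blocked by site and sites still differ after baseline adjustment

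*SAP*

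**What the plan says.** SAP 2.4 describes random assignment "in a 1:1 ratio at each site", using pre-numbered bottles. The pharmacist is to "dispense the next number in sequence to the next patient who qualifies for the study at an individual site". Protocol v5.0, section 11.5, describes a scheme "to ensure subjects are randomly assigned to SOC + brequinar or SOC + placebo in a 1:1 ratio" and does not name site. Neither document gives a block size or says that the list is stratified.

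For the primary analysis, SAP 7.6.1 states: "The model will contain baseline as a covariate, treatment, day and treatment-by-day interaction as fixed effects". It is run in the Microbiology Evaluable Set (MES), a subset of those randomised. For the main secondary endpoint, SAP 7.6.2 states: "Duration of viral shedding will be compared between treatment groups using a unstratified log rank test". Hospital admission and death are compared by Fisher's exact test. Site enters only as a sort order for listings and as a count in SAP 7.2: "A summary of subject enrollment by site will also be provided".

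On centres, protocol 11.6 says only: "Not applicable to this small, early phase study". The synopsis gives the number of sites as "Approximately 15".

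**The concern.** When allocation is forced to balance within a factor, differences between levels of that factor largely cancel out of the treatment comparison. A model that omits the factor leaves those differences in its residual variance, so it reports a larger standard error than the design delivers. Intervals are then too wide and tests conservative. The protocol's remark on pooling centres does not say why a factor used in allocation should be left out of the model.

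What is at stake is precision. The trial has about 100 subjects, a smaller primary analysis set and no power calculation. Its stated purpose is to inform later study design, so the width of the intervals is a large part of what it produces. Protocol 8.9 itself expects available treatment to change over time and to differ between sites. Baseline viral load need not capture that kind of site difference.

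**Working it through.** **Inputs from the documents.** About 100 subjects and about 15 sites (100/15 = 6.7 per site); 1:1 allocation; two-sided 5% tests; baseline viral load in the model. The documents give no effect size, SD, power or ICC, so there is no planned figure to reproduce.

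**Assumptions.** Residual ICC ρ (the between-site share of variance after baseline adjustment) from 0 to 0.20; permuted blocks of 2, 4 or 6 within site; residual SD 1.

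**Step 1: exact balance within site.** The true variance of the treatment difference is 4σ²(1−ρ)/N. The site-free model reports about 4σ²/N. The ratio of reported to true SE is 1/√(1−ρ). With N = 100 and σ = 1 the reported SE is √(4/100) = 0.200.

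| ρ | True SE | Ratio | Actual two-sided error rate |
|---|---|---|---|
| 0.05 | √0.038 = 0.195 | 1.026 | 4.4% |
| 0.10 | √0.036 = 0.190 | 1.054 | 3.9% |
| 0.20 | √0.032 = 0.179 | 1.118 | 2.8% |

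This is the ceiling. Small sites with incomplete blocks are not exactly balanced.

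**Step 2: simulation with small sites.** 4,000 trials per setting, 15 unequal sites, one post-baseline visit with complete data, ANCOVA on baseline. Ratio of reported to empirical SE for the model without site (Monte Carlo error about 1%):

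| ρ | Not blocked | Blocks of 2 | Blocks of 4 | Blocks of 6 |
|---|---|---|---|---|
| 0 | 0.985 | 1.019 | 0.981 | 0.996 |
| 0.05 | 1.012 | 1.031 | 1.027 | 1.012 |
| 0.10 | 0.991 | 1.049 | 1.039 | 1.031 |
| 0.20 | 1.011 | 1.107 | 1.096 | 1.064 |

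At ρ = 0.20 the error rate under blocking was 2.9% to 3.6%. A repeat at blocks of 4 with a 0.5 SD effect gave ratios of 1.012, 1.066 and 1.090 at ρ = 0.05, 0.10 and 0.20, so the bands are good to a percentage point or two. With an assumed random 70% MES the ratio was 1.03-1.05 at ρ = 0.10 and 1.07-1.08 at 0.20.

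The excess disappears in two cases: when the list is not blocked (ratios 0.99-1.01), and when sites differ only through baseline viral load (1.005 at blocks of 4).

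**Step 3: fixed or random site effects.** Fixed effects for 15 sites use 14 degrees of freedom. For a 0.5 SD effect with blocks of 4, power without and with fixed site effects was 68.1% and 66.7% at ρ = 0, 70.6% for both at 0.05, 70.5% and 72.7% at 0.10, and 71.3% and 76.0% at 0.20. Fixed effects therefore cost a little when sites do not differ.

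A random intercept avoids that loss. Power without and with a restricted maximum likelihood (REML) site intercept, 2,000 trials per setting, assumed effect 0.56 SD:

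| ρ | Blocks of 4 | Not blocked | Blocks of 4, 70% MES |
|---|---|---|---|
| 0 | 80.1 → 80.3% | – | – |
| 0.05 | 78.5 → 79.9% | – | – |
| 0.10 | 79.3 → 82.0% | 77.5 → 80.5% | 63.5 → 65.6% |
| 0.20 | 81.6 → 85.9% | 82.1 → 86.0% | 64.6 → 70.8% |

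Monte Carlo error is about 0.9 points on each power. A repeat with 1,500 trials at blocks of 4 gave 78.4 → 78.6% at ρ = 0, 79.6 → 82.1% at 0.10 and 82.1 → 87.3% at 0.20. At blocks of 4 in the full set, the gains are therefore 1.4 points at 0.05, 2.5 to 2.7 at 0.10 and 4.3 to 5.2 at 0.20.

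**The case against.** A reader might infer that the primary standard errors are too wide whenever sites differ. The documents do not support that, because two conditions are needed and neither is established. First, the list must force balance within site. The SAP's wording suggests this, but no block size is stated and protocol 11.5 names no site stratum. Second, the site differences must survive adjustment for baseline viral load, which is already in the model.

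A reader might also infer a risk of false positives. The error runs the other way, and protocol section 11 declares any testing exploratory and descriptive.

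The documents also limit how large the site effect is likely to be. Saliva is self-collected and assayed at one central laboratory, follow-up is by home visit or telemedicine, and symptom onset must be within 7 days of first dose. Varying standard of care is the one route to a site effect that the protocol names. All of this stands, and it keeps the point small.

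The remedy has costs of its own. It adds one variance parameter to a model whose unstructured covariance may already fail to converge, and it assumes the same site effect at all six visits. Dropping the term when its variance is zero is a data-driven rule: at ρ = 0 the variance was estimated as zero in only about 57% of simulated trials, so the term often stays in. In the 70% MES runs the error rate was 4.4-6.7% with the intercept and 3.9-5.8% without it. That is why a small-sample degrees-of-freedom method belongs in the specification.

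It may seem inconsistent to leave the log-rank and Fisher tests unstratified. The case for the intercept is a cheap gain in precision, however, and stratifying those tests by 15 sites of six or seven subjects would not be cheap.

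**Conclusion.** The point holds in conditional form. SAP 2.4 balances allocation at each site and no outcome analysis uses site. Given blocking by site and residual site differences, the planned primary standard errors are too wide by about 1-3% at ICC 0.05, 3-5% at 0.10 and 6-11% at 0.20. Without blocking they are correct, but a site term would still improve precision if sites differ, so the recommendation does not depend on how the list was built.

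The sizes rest on an assumed ICC, assumed block sizes, an assumed 70% MES where that is quoted, and simulation of a single visit with complete data in place of the full repeated-measures model. Below an ICC of about 0.05 the gain is negligible. Priority is low: the plan as written is valid and slightly conservative.

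**What to change.** In SAP 7.6.1, add a random intercept for site to the MMRM and specify a small-sample degrees-of-freedom method such as Kenward-Roger. State that the intercept is removed only if its variance is estimated as zero or the model fails to converge, and place that step within the existing fallback sequence for the covariance structure. In SAP 2.4, state whether and how the list is blocked by site, and reconcile this with protocol 11.5. The log-rank and Fisher tests can stay as they are.

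The cost is one extra model statement and a few sentences in the SAP, agreed before unblinding. No new data are needed. The downside is one more variance parameter, a slight convergence risk and the assumption of a common site effect across visits. If sites do not differ, essentially no power is lost.

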3.1 Primary Efficacy Endpoint

- Quantitative SARS-CoV-2 viral load through Day 29

3.2 Secondary Efficacy and Clinical Endpoints

Through Day 29:

- Duration of viral shedding;
- Percentage of subjects requiring admission as an inpatient for >24 hours;
- All-cause mortality.

3.3 Exploratory Efficacy and Clinical Endpoints

Through Day 29:

- Time to viral clearance (two consecutive undetectable tests);
- Viral culture through Day 29;
- Time to resolution of new onset COVID-19-related clinical symptoms and pre-existing non-COVID-19 symptoms returned to baseline;

Statistical Analysis Plan

Sponsor Name: Clear Creek Bio, Inc.
Sponsor Protocol ID: CCB-CRISIS-02

Covance Study ID: 000000207395

- Time to clinical improvement measured by a favorable shift in WHO Ordinal Scale score for the subset of subjects with baseline WHO Ordinal Scale of 2 or 3.

3.4 Safety Variables

- Rates of AEs and SAEs;
- Laboratory assessments through Day 29;
- Vital signs through Day 29.

4. Pharmacokinetic/Pharmacodynamic variables

Not applicable.

5. Analysis populations

5.1 Screened

All subjects who consent to participate and who undergo screening will be included in the Screened population.

5.2 Safety Analysis Set

The Safety Analysis Set (Safety) will consist of all subjects who received at least one dose of study drug. Safety analysis subjects are analyzed according to their actual treatment received.

5.3 Intent-to-treat Set

The Intent-to-treat Set (ITT) will consist of all randomized subjects. ITT subjects are analyzed according to their randomized treatment.

5.4 Microbiology Evaluable Set

The Microbiology Evaluable Set (MES) will consist of all randomized subjects with detectable SARS-CoV-2 viral load at baseline and at least one non-missing post-baseline viral load assessment. Microbiology evaluable subjects are analyzed according to their randomized treatment.

5.5 Per Protocol Set

Not applicable.

6. Data Handling

6.1 Time points and Visit Windows

Day 1 is defined as the day of first dose of study drug. Relative days after Day 1 are calculated as (assessment date – Day 1 date) + 1. Relative days prior to Day 1 are calculated as (assessment date – Day 1 date). The day prior to Day 1 is Day -1.

All data will be analyzed using nominal study visits as defined in the Study Schedule and eCRF. No visit windows will be applied for summary and analysis.

6.2 Handling of Dropouts, Missing Data, and Outliers

A subject may withdraw from the study at any time for any reason. The Sponsor or Investigator may also terminate a subject's study participation after discussion with the other party if it is believed it would be unsafe for the subject to continue in the study. All scheduled evaluations will be collected/conducted even for subjects who discontinue study medication prior to completing the treatment period unless consent is withdrawn.

Missing efficacy data will not be imputed except for the automatic imputation done by the statistical modeling. Viral load values of the form of "<x" (i.e. below the lower limit of quantification) will be imputed as "x" in the analysis of viral load changes but displayed as "<x" in the listing.

Missing safety data will generally not be imputed. However, laboratory values of the form of "<x" (i.e. below the lower limit of quantification) or ">x" (i.e. above the upper limit of quantification) will be imputed as "x" in the calculation of summary statistics but displayed as "<x" or ">x" in the listings. Additionally, AEs that have missing causality (after data querying) will be assumed to be related to study drug.

If start date of a prior/concomitant medication is partially missing, impute as follows:

- If both Month and Day are missing, then set to January 1
- If only Day is missing, then set to the first day of the month

If end date of a prior/concomitant medication is partially missing, impute as follows:

- If both Month and Day are missing, then set to December 31
- If only Day is missing, then set to last day of the month

If start date and/or end date of a prior/concomitant medication is completely missing, do not impute.

Listings will present the actual partial dates; imputed dates will not be shown.

No rules for outlier detection are planned.

Statistical Analysis Plan

Sponsor Name: Clear Creek Bio, Inc.
Sponsor Protocol ID: CCB-CRISIS-02

Covance Study ID: 000000207395

7. Statistical Methods

7.1 General Principles

All data processing, summarization and analyses will be performed using Covance's SAS Environment / Version 9.3 (or later) of the SAS® statistical software package.

The following principles will be applied to all tables, figures, and listings (TFLs) unless otherwise stated:

Principle	Value
Significant tests	Two-sided and use a 5% significance.
Treatment group labels and order presented	SOC + Brequinar 100 mg SOC + Placebo
Tables	Data in summary tables presented by treatment group, assessment and visit (where applicable), unless otherwise specified.
Listings	All data collected presented by treatment group, site, subject, assessment and visit (where applicable), unless otherwise specified.
Descriptive summary statistics for continuous variables	Number of subjects/observations (N), mean, standard deviation (SD), median and range.
Descriptive summary statistics for categorical variables	Frequency counts and percentages [n (%)]
Denominator for percentages	Number of subjects in the analysis population, unless stated otherwise in table shell(s)
Include "Missing" as category	Yes, when the number missing is greater than zero for at least one treatment group.
Display for 0 percentages	Blank
Display to one more decimal place than collected value	Mean Standard Error Mean Difference Median
Display to two more decimal places than collected value	Standard Deviation Confidence Interval
Limit of precision for displays	3 decimal places
Date Format	DDMMYYYY
Dictionary names and versions	The dictionary names and versions will be included in a footnote in all AE, medical history, prior and concomitant medication TFLs that present coded terms from the dictionaries.

Time to event or duration of event endpoints will be based on the actual date rather than Visit Day.

7.2 Subject Disposition and Data Sets Analyzed

Subject disposition will be listed and summarized by treatment group and overall and will include the number and percentage of subjects:

- screened;
- randomized;
- randomized and not treated;
- treated;
- included in each analysis population (ITT, MES, Safety).

In addition, the number and percentage of subjects who complete the study and who discontinue early, including a breakdown of the primary reasons for discontinuation, will be presented for ITT population.

A summary of subject enrollment by site will also be provided.

A summary of the reasons for screen failure as well as the number of subjects screened but not randomized will be produced. No other information for screen failures will be presented.

7.3 Protocol Deviations

Protocol deviation management process, including project specific protocol deviations list, deviation detection, management and escalation, and review of protocol deviations, is defined in the Protocol Deviation Management Plan. Protocol deviations will be identified before data are unblinded. All protocol deviations will be listed. Important protocol deviations will be summarized by treatment group for the ITT population.

7.4 Demographics and Other Baseline Characteristics

Demographics will be listed and summarized by treatment group and overall for the ITT population. Standard descriptive statistics will be presented for the continuous variables of:

- age (years) [calculated as (year of informed consent – year of birth) if age is not recorded on the eCRF];
- weight (kg);
- height (cm);
- body mass index (kg/m²) [calculated as (weight/height²) where weight is in kg and height is in m].

Statistical Analysis Plan

Sponsor Name: Clear Creek Bio, Inc.
Sponsor Protocol ID: CCB-CRISIS-02

Covance Study ID: 000000207395

The total counts and percentages of subjects will be presented for the categorical variables of:

- age group (years) (grouped as <65, \geq 65);
- gender;
- race;
- ethnicity.

In addition, baseline characteristics collected prior to the first dose of study drug will be listed and summarized by treatment group and overall for the ITT population. Standard descriptive statistics will be presented for the continuous variables of:

- temperature ($^{\circ}$ C);
- oxygen saturation, SpO₂ (%);
- respiratory rate (breaths/min).

The total counts and percentages of subjects will be presented for the categorical variables of:

- SARS-CoV-2 viral load (detectable, undetectable);
- COVID-19 symptom type;
- WHO Ordinal Scale.

No formal tests of statistical significance will be performed on the demographic and baseline data.

Other baseline measurements, such as vital signs, laboratory results will be summarized by treatment group with the post-baseline measurements.

